2. OBJECTIVES

Primary Objective

We aim to measure safety and efficacy of intravenous treatment with acyl-ghrelin to promote cerebral recovery in comatose patients after cardiac arrest. Safety will be monitored throughout hospitalization and during follow-up using all AEs reported, and by interim analyses by an independent DSMB. Efficacy will be measured by the primary outcome measure, i.e. functional recovery as measured by the Cerebral Performance Category (CPC) scale at six months after cardiac arrest.

Secondary Objective(s):

To measure safety and efficacy of ghrelin to modify

1. Case fatality
2. Time to awaken (time interval between resuscitation and Glasgow Coma Scale (GCS) score of 14)
3. Long term outcome: CPC and cognitive functioning at 12 months
4. Cardiovascular measures:

Mean arterial blood pressure day 1-7 (mean, highest, lowest)

Heart rate day 1-7 (mean, highest, lowest)

Arrhythmia day 1-7: yes / no. If yes: type of arrhythmia

Cumulative dose of vasopressive medication day 1-7

Cumulative dose of inotropic medication day 1-7

Sequential Organ Failure Assessment score day 1-7

Kidney function day expressed as GFR day 1-7

CVVH day 1-7: yes / no

Assist devices day 1-7: yes / no

5. Biomarkers

Cardiac: troponine and CK / CK-MB ratio at day 0, 1, 2 or 3

Neurological: NSE day 1, 2, 3

Endocrinological: cortisol, growth hormone, prolactine, ACTH, IGF-1 day 1, 2, 3

Highest glucose levels at day 1-7

6. Gastro-intestinal: gastric residual volume (day 1-7, during ICU admission)

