After randomization, daily physical, neurological, and additional examinations at the ICU will be part of routine patient care. In addition, there will be blood sampling for measurement of ghrelin concentrations at day 1 and 3, measures of neuronal damage (NSE at day 1-3), measures of cardiac damage (troponine and CK/CK-MB ratio at day 0-3), hormone concentrations (cortisol, growth hormone, prolactine, ACTH, IGF-1 at day 1-3), and highest glucose levels at day 1-7. All blood samples will be collected during routine blood sampling, if possible; preferably, there will be no additional punctures. However, blood sampling for measurement of ghrelin concentrations will be done at 30±15 minutes after treatment with ghrelin or placebo. For these measurements additional blood samples will be taken, if necessary.

Apart from the study treatment and the venous blood sampling, patients will not be subjected to additional procedures during admission.

Surviving patients will be asked informed consent for participation and additional follow-up on long term outcome. Follow up at 3 and 6 months in surviving patients will be done by telephone interview by a trained research nurse three and six months after admission. The nurse will collect CPC scores based on a standard interview. At twelve months, patients will be invited to the nearest hospital or visited at their place of residence for detailed neuropsychological examination (please see F1 testbatterij NPO for details of the test

battery). Separate informed consent will be asked for neuropsychological examination at twelve months.

Table. Overview of study procedures

	Baseline (Day 0)	Day 0-6	Day 1-7	Day 7	3m	6m	12m
Ghrelin/ placebo treatment		X					
Venous blood sampling (largely within current care)	X		X				
CPC scores				X	X	X	
Neuropsychological examination							X

M = months, CPC = Cerebral Performance Category, to be collected by a telephone interview

The total burden in hours for the patient is max 12 hours. This includes multiple transfusions of the study drug, venous blood sampling, and the follow-up procedures at 3, 6 and 12 months.

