8.2 AEs, SAEs and SUSARs

8.2.1 (Serious) Adverse events reporting

As this is a randomised controlled trial with a new drug all (serious) adverse events mentioned in paragraph 8.2.2 and 8.3.3 are required to be reported to the Sponsor and recorded in the electronic database. The sponsor is responsible to report the SAE to the accredited METC that approved the protocol.

Reporting of SAEs will be the responsibility of the study coordinator and the principle investigator. The local principle investigators will report on AEs, SAEs and SUSARs within the relevant time windows mentioned below. A dedicated study nurse will collect all AEs, SAEs, and SUSARs and discuss these with the principle investigator, every week.

Since case fatality in the patient population under study is known to be 50-60%, with most deaths occurring in the first week of ICU admission, line listing of all SAEs including deaths is requested, with reporting to the accredited METC once per two months. Exceptions will be made for (1) the first ten inclusions in the trial, (2) SAEs that are probably related to the trial, and (3) Suspected Unexpected Serious Adverse Reactions, for which expedited reporting will take place.

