9. STATISTICAL ANALYSIS

9.1 Primary study parameter(s)

The primary analysis will be a single comparison between the treatment groups of the primary outcome measure after six months. This analysis will be performed according to the intention-to-treat principle. To assess the effect of treatment with ghrelin, the whole range of the CPC will be taken into account. This indicates that no dichotomy will be used in the primary analysis. Instead of a dichotomy, any shift in the direction of a better

outcome on de CPC scale will be analyzed. This will be expressed as a common odds ratio for improvement.²⁷

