9.2 Secondary study parameter(s)

With regard to the range of secondary outcome parameters, we will use simple 2x2 tables, two-group t-tests, Mann-Whitney tests, or multivariable linear and logistic regression models, where appropriate. In all analyses, statistical uncertainty will be quantified by means of 95% confidence intervals. Subgroup analyses based on the EEG pattern at 24 hours will be carried out for the following subgroups: (1) suppressed patterns and suppressed patterns with synchronized periodic activity, (2) continuous patterns, and (3) other patterns. This is based on our previous studies on EEG based outcome prediction of comatose patients after cardiac arrest, where the first subgroup represents patterns that are strongly associated with a poor prognosis, the second subgroup with a good prognosis, and the third subgroup with an intermediate prognosis.[refs] Although the size of this study will not allow for precise estimates of treatment effect in subgroups, we will assess heterogeneity of effects, and analyze consistency of effects on secondary outcomes.

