10.2 Recruitment and consent

Patients will be recruited at intensive care units at the participating hospitals. The treating intensivist / neurologist / clinical neurophysiologist will check the in- and exclusion criteria, inform a patient's legal representative, and ask for informed consent. Since any beneficial effect of the treatment under study is assumed to be larger with earlier initiation, treatment should be initiated within 12h after cardiac arrest, and as soon as possible after ICU admission. All participating centers have ample experience with inclusion of patients with acute cardiac arrest or cerebral ischemia in intervention studies. Survivors will be asked for informed consent for long term follow up (6 and 12 months) separately.

Written informed consent, documented on the informed consent form in accordance with GCP standards and study centre regulations, shall be obtained from each patient or its legal representative. First, a short version of the informed consent will be used to start the treatment within 12 hours after resuscitation. The more extensive patient information will be obtained within 48 hours after the start of trial treatment. The legal representative should sign this informed consent form as well. The original signed form will be kept in the Investigator Site File. The PI will retain a copy of the signed informed consent form in each patient's study record, and provide a copy to the patient or its legal representative.

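### Cognitive functioning at 12 months is scored only in consenting, testable survivors, so a two-group comparison of the scores is selected after randomisation and can be biased in either direction

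*Protocol*

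**What the plan says.** Section 2 of the protocol lists among the secondary objectives "Long term outcome: CPC and cognitive functioning at 12 months", under a lead-in on safety and efficacy. Section 7.1.2 repeats both items as secondary endpoints.

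Section 7.3 sets out how cognition is obtained: "At twelve months, patients will be invited to the nearest hospital or visited at their place of residence for detailed neuropsychological examination". Two consent steps come first. The same section states "Surviving patients will be asked informed consent for participation and additional follow-up on long term outcome" and then "Separate informed consent will be asked for neuropsychological examination at twelve months". Section 10.2 agrees: "Survivors will be asked for informed consent for long term follow up (6 and 12 months) separately".

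Section 8.2.1 gives the expected mortality: "Since case fatality in the patient population under study is known to be 50-60" per cent, with most deaths in the first week of ICU admission.

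For the analysis, section 9.2 says of all secondary outcomes that "we will use simple 2x2 tables, two-group t-tests, Mann-Whitney tests, or multivariable linear and logistic regression models, where appropriate". Section 9.1 says "This analysis will be performed according to the intention-to-treat principle", but this refers to the primary analysis.

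The procedures table in section 7.3 marks CPC at day 7, 3 months and 6 months. At 12 months it marks only the neuropsychological examination. Section 7.1.2 lists case fatality at one week and at 6 months.

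**The concern.** A patient has a 12-month cognitive score only after surviving, consenting again and completing a detailed battery. Treatment may affect all three. The protocol does not say in words that untestable survivors are left out; that follows from using a test battery as the measure.

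The patients with scores in the two arms are therefore not the randomised groups. If ghrelin changes who survives, the arms contribute different kinds of survivor, and a difference in mean score mixes the effect on cognition with the effect on who can be measured. A confidence interval around that difference does not cover this error.

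The schedule makes the result harder to interpret. No 12-month CPC is scheduled although sections 2 and 7.1.2 list it, and no 12-month item separates a survivor too impaired to be tested from one who declined.

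**Working it through.** **The plan's own figure.** The only sample size is for the primary endpoint (section 4.4: difference 0.8, SD 1.8, alpha 0.05, power 80%). Two-sided, n per arm = 2 × (1.960 + 0.842)² × 1.8² / 0.8² = 79.5, so 80 per arm and 160 in total. This reproduces. No figure is given for the cognitive endpoint.

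**How many can have a score.** Section 8.2.1 gives case fatality without a time point; I apply it to 12 months. Later deaths would lower the counts.
- Fatality 50%: 160 × 0.50 = 80 survivors.
- Fatality 60%: 160 × 0.40 = 64 survivors.
- If 80% of survivors consent and can be tested (assumption): 51 to 64. If 60% (assumption): 38 to 48.

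**Size of the possible bias.** Assume a standard normal survival tendency in which the lowest share F die, and correlation ρ between that tendency and cognition. Assume also that every survivor is tested and that the drug has no effect on cognition. With t = Φ⁻¹(F):
- mean tendency among survivors: m(F) = φ(t)/(1 − F)
- variance among survivors: v(F) = 1 + t·m − m²
- apparent difference, ghrelin minus placebo, in SDs of placebo survivors' scores: ρ[m(F₁) − m(F₀)] / √(1 − ρ²(1 − v(F₀)))

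Placebo fatality is set at F₀ = 0.55, the middle of the protocol's range, and the 10-point change is assumed. Then m(0.55) = 0.880, m(0.45) = 0.720, m(0.65) = 1.058 and v(0.55) = 0.337. At ρ = 0.5 with mortality falling to 45%: 0.5 × (−0.160) / √(1 − 0.25 × 0.663) = −0.080/0.913 = −0.088.

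| Assumed ρ | Mortality 55% to 45% | Mortality 55% to 65% |
|---|---|---|
| 0 | 0 | 0 |
| 0.3 | −0.049 | +0.055 |
| 0.5 | −0.088 | +0.098 |
| 0.7 | −0.136 | +0.152 |
| 1.0 | −0.276 | +0.308 |

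**A cruder cross-check.** Suppose 50% of placebo patients are tested, and ghrelin adds 10 points of tested survivors who score 1 to 1.5 SD lower. The shift is 0.10 × (−1)/0.60 = −0.17 to 0.10 × (−1.5)/0.60 = −0.25 SD. This lies in the upper part of the range above.

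**If the drug also helps cognition.** The fall from 55% to 45% is a shift of 0.251 on the survival tendency. If cognition improves by the same amount, the net survivor difference is 0.251 − 0.160ρ, or +0.20 (ρ = 0.3) to +0.09 (ρ = 1.0) latent SD. At half that improvement it is +0.08 to −0.03.

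**Against sampling error.** The standard error in SD units is √(2/n per arm): 0.22 with 40 tested per arm, 0.24 with 36 and 0.25 with 32.

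**The case against.** How deaths and missing scores enter a secondary endpoint is commonly settled in a statistical analysis plan, and that plan is not shown. Section 9.2 does not prescribe a survivor-only t-test of cognition; it lists methods for all secondary outcomes, to be used as suitable. Rules for untestable patients may also stand in the separate test-battery document. Home visits reduce loss among disabled survivors. Case fatality and CPC would be reported in the same trial, so the cognitive result need not be read alone.

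Much of this stands, and the absence of an analysis rule is not the point here. An analysis plan cannot recover information that was never collected, however, and the protocol fixes what is collected. Section 8.2.4 requires the date and cause of death, and section 8.4 continues SAE reporting to the end of the study, so deaths can probably be identified. What the schedule does not provide is a 12-month record of why a living patient has no score. The outcomes offered as reassurance are weakest at that time point: the table schedules no 12-month CPC, and case fatality as an endpoint ends at 6 months.

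A reader might infer more: that a drug which saves severely injured patients will look harmful to cognition and a lethal one beneficial. The documents do not support that certainty.
- It needs the rescued patients to be testable and to score lower than the others. If they are too impaired to be tested, they cannot lower the ghrelin mean. The comparison then omits the worst cognitive outcomes, which is a different fault.
- It needs little or no direct benefit to cognition. The protocol's hypothesis is protection of the brain itself, which works the other way.
- The bias is mostly below or near one standard error, so a misleading significant result is possible but not expected.

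A reader might also take section 2 to promise a comparison of all randomised patients on cognition. It does not say so.

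**Conclusion.** The concern holds as a risk of bias in either direction. On the protocol's own fatality figure, at least 80 to 96 of the 160 patients cannot have a 12-month cognitive score, and those who can are selected after randomisation.

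The size of the bias rests on assumptions that the protocol does not supply: a 10-point mortality difference, the correlation between survival and cognition, all survivors tested and no direct cognitive effect. Under these it is roughly 0.05 to 0.3 SD in absolute size for correlations of 0.3 to 1.0, and zero at no correlation, against a standard error of about 0.2 to 0.25 SD.

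The endpoint is secondary and the primary analysis is not touched. The change should still be made, because it is cheap and the reason for a missing score is hard to reconstruct later.

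**What to change.** 1. In section 7.3 and the eCRF, record one 12-month status for every randomised patient: dead; alive but untestable because of impairment; declined or lost; tested. Report the counts by arm beside the cognitive results.
2. In section 9.2, state that scores in tested survivors are descriptive and are not a randomised efficacy comparison.
3. Optionally, add a sensitivity analysis with the Mann-Whitney test that section 9.2 already lists. Rank death worst, then untestable, then one summary score named in advance from the battery, with declined or lost treated as missing. State that mortality mainly drives this ranking: with 40-50% surviving, only 0.40 × 0.40 = 16% to 0.50 × 0.50 = 25% of between-arm pairs compare two survivors. For that reason it should not be the main cognitive analysis.

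The cost is one eCRF item, a short wording change and the loss of a formal survivor-only test. Selection through refusal remains, but it becomes visible by arm.

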7.4 Withdrawal of individual subjects

Subjects can leave the study at any time for any reason if they wish to do so without any consequences.

7.5 Replacement of individual subjects after withdrawal

Subjects will be replaced after withdrawal for any reason.

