7.2 Randomisation, blinding and treatment allocation

Subjects after cardiac arrest and successful cardiopulmonary resuscitation that are admitted to an intensive care unit of a participating hospital can be considered for enrolment in the study. Randomisation will be 1:1, in blocks of N=10, stratified by study site. Randomisation will be performed if the subject meets all inclusion/exclusion criteria and will be processed centrally by means of a web-based system that will provide the randomisation treatment arm (Ghrelin or placebo). The online system (Research Manager®), is constructed and validated for randomization and data management and has an audit trail. Contact persons of all participating centres can sign in and randomize their patients.

A legal representative or family member will be informed and patients will be included on the intensive care by their treating intensive care physician. Once informed consent is obtained, the collaborating hospital pharmacist will be notified by the intensive care physician. The pharmacist will sign in Research Manager, include the patient and randomize. The pharmacist will receive the treatment allocation through Research Manager, and thus be unblinded. He / she will prepare the treatment or placebo and provide it to the treating intensive care physician. The intensive care physician will remain blinded to the treatment allocation.

The investigator can decide to withdraw a subject from the study for urgent medical reasons. In this case the investigator can decide to 'unblind' the patient. For unblinding, the unblinded collaborating pharmacist will provide information on the treatment allocation to the treating intensive care physician.

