7.6 Follow-up of subjects withdrawn from treatment

Every attempt will be made to complete the primary follow-up in these patients.

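### Section 7.5 replaces withdrawn patients without saying that they stay in the primary analysis, and so permits a departure from the intention-to-treat analysis in 9.1

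*Protocol*

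**What the plan says.** Section 7.5 of the protocol consists of one sentence: "Subjects will be replaced after withdrawal for any reason". It sets no limit on reason, timing or number. It does not say whether the replaced patient remains in the analysis.

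Section 9.1 says of the primary comparison of six-month CPC: "This analysis will be performed according to the intention-to-treat principle".

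There are several routes out of the trial:
- Section 7.4, the patient's own choice: "Subjects can leave the study at any time for any reason if they wish to do so without any consequences".
- Section 7.2, the investigator's choice: "The investigator can decide to withdraw a subject from the study for urgent medical reasons". The same paragraph lets the investigator unblind in that case.
- Sections 7.3 and 10.2, a consent step that only survivors reach: "Surviving patients will be asked informed consent for participation and additional follow-up on long term outcome" and "Survivors will be asked for informed consent for long term follow up (6 and 12 months) separately". The six-month assessment named there is the primary endpoint.

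Section 7.6, whose heading confines it to patients withdrawn from treatment, says: "Every attempt will be made to complete the primary follow-up in these patients". No such sentence covers patients who leave, or are taken out of, the study.

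**The concern.** In ordinary usage, a replaced patient gives up his or her place to a new one. Section 4.4 fits that reading: it has no allowance for lost outcomes, so replacement is the only stated means of holding the trial at 160. A site or data manager could reasonably take 7.5 to mean that the withdrawn patient no longer counts and need not be followed.

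The withdrawals may not be random with respect to outcome. Withdrawal for urgent medical reasons follows deterioration, and allocation may become known at that point. Refusal of follow-up is open only to survivors, so every loss there comes from CPC 1 to 4. If such patients drop out of the comparison at different rates in the two arms, the protection given by randomisation is lost. An analysis plan written later cannot recover outcomes that were never collected.

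**Working it through.** **Inputs from section 4.4.** Control mean CPC 3.20, SD 1.8, difference 0.8, alpha 0.05, power 80%, N = 160.

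**1. The plan's own figure.** Per arm, n = 2 × (1.960 + 0.842)² × 1.8² / 0.8² = 2 × 7.85 × 5.0625 = 79.5, rounded up to 80, so 160 in total. Power at 80 per arm is 80.3%. The sidedness of alpha is not stated; two-sided reproduces 160, while one-sided gives 126. There is no inflation for lost outcomes.

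**2. Replaced patients kept and followed.** Everyone randomised is analysed as allocated. The number randomised rises above 160 and there is no bias from the rule. To keep 160 observed outcomes at an assumed loss of 5% or 10%: 160/0.95 = 168.4, so 169; 160/0.90 = 177.8, so 178.

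**3. Replaced patients left out.** The protocol gives neither a withdrawal rate nor a full CPC distribution, so both are assumed. A smooth distribution fitted to mean 3.20 and SD 1.8 puts 34.1%, 8.0%, 5.2%, 9.1% and 43.6% in CPC 1 to 5. (Its 43.6% in CPC 5 is below the 50-60% case fatality in 8.2.1, so it is illustrative only.) There is no true treatment effect. Each arm is refilled to 80 retained patients.

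If a fraction w of a group with share s and mean m is lost, the retained mean is (3.20 − w·s·m)/(1 − w·s).

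- Survivors (CPC 1-4): s = 0.564, s·m = 3.20 − 5 × 0.436 = 1.02. Lost in the placebo arm only:
  - w = 10%: (3.20 − 0.102)/0.9436 = 3.283, a shift of 0.08.
  - w = 20%: (3.20 − 0.204)/0.8872 = 3.377, a shift of 0.18.
- CPC 4-5: s = 0.527, s·m = 4 × 0.091 + 5 × 0.436 = 2.544. Lost in the ghrelin arm only:
  - w = 10%: (3.20 − 0.254)/0.9473 = 3.109, a shift of 0.09.
  - w = 20%: (3.20 − 0.509)/0.8946 = 3.008, a shift of 0.19.

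All four shifts favour ghrelin; with the arms exchanged they would favour placebo. Per 80 randomised, the losses are about 4 to 9 patients in the affected arm (80 × 0.527 × 0.10 = 4.2; 80 × 0.564 × 0.20 = 9.0).

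Type I error, from 4,000 simulated trials per scenario with a two-sided Mann-Whitney test:

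| Assumed withdrawal, replaced patients excluded | Shift (CPC points) | Type I error |
|---|---|---|
| None | 0 | 4.8% |
| Survivors, 10% in both arms | 0 | 4.6% |
| Survivors, 10% placebo only | 0.08 | 5.3% |
| Survivors, 20% placebo only | 0.18 | 10.2% |
| CPC 4-5, 10% ghrelin only | 0.09 | 6.1% |
| CPC 4-5, 20% ghrelin only | 0.19 | 10.6% |

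The simulation standard error near 5% is √(0.05 × 0.95/4000) = 0.3 percentage points, so 5.3% is not distinguishable from no inflation.

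**4. Nobody replaced, lost outcomes missing.** With 80 × 0.95 = 76 or 80 × 0.90 = 72 per arm, power is 78.2% or 76.0%.

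**The case against.** The strongest reply is that intention-to-treat governs who is analysed and in which arm, and does not forbid recruiting more patients. The protocol nowhere says that replaced patients are excluded. Section 9.1 commits to intention-to-treat, and 7.6 pursues the primary outcome after withdrawal from treatment, which would be pointless if those patients were discarded. Recruiting further patients is an understandable way to keep about 160 observed outcomes when 4.4 has no allowance for loss. All of this stands, so a reader who infers that 7.5 contradicts 9.1 goes further than the text.

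Three other inferences also fail:
- **Outcome-related withdrawals are swapped within an arm.** No same-arm or one-for-one substitution is described. Under 7.2 a new patient would be randomised 1:1 in site-stratified blocks.
- **The damage cannot be repaired.** That is true only where the outcome was never obtained. If patients are followed, they can be analysed.
- **Refusal by survivors is a consequence of 7.5.** If 15% of survivors in one arm and 5% in the other declined (assumed), the survival odds ratio among those observed would be multiplied by 0.85/0.95 = 0.89. That would happen with no replacement rule at all. It is a missing-data question, which an analysis plan may address.

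The treating physician is also blinded by default, so strongly one-sided withdrawal is not the expected case. What the reply does not answer is the gap itself: 7.6 does not reach patients who leave the study, 7.5 replaces them, and nothing says that they still count.

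**Conclusion.** The point holds as a permissive and incomplete rule. Section 7.5, read in its ordinary sense, lets patients whose withdrawal is related to outcome leave the primary comparison, and the protocol does not rule this out.

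Bias requires two conditions together: replaced patients are left out, and withdrawal differs by arm. Under the assumed one-sided rates, the shift is roughly a tenth to a quarter of the 0.8-point design difference (0.083/0.8 = 10%; 0.192/0.8 = 24%). Type I error is barely affected at 10% and about doubled at 20%. If either condition fails, this bias is absent. These figures rest on assumed rates and a fitted distribution; they show what the rule could allow and do not forecast what will happen.

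**What to change.** Reword 7.5 along these lines: *Every randomised patient remains in the intention-to-treat analysis in the allocated arm, whether or not a further patient is recruited. Stopping study treatment does not lead to replacement. Further recruitment is limited to patients whose primary outcome cannot be obtained, for example because consent to use of data is withdrawn, and is reported by arm.*

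Extend 7.6 so that follow-up to six months, at least vital status and CPC where consent permits, also continues for patients withdrawn by the investigator under 7.2. The clinical decision to stop treatment is left as it is.

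The cost is mainly wording, but there is a price in numbers that the protocol should state. Either the number randomised exceeds 160 (169 or 178 at an assumed 5% or 10% of outcomes lost), or nobody is replaced and power falls from 80.3% to about 78% or 76%.
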